8.3 Definition of a Serious Adverse Event (SAE)

A Serious Adverse Event (SAE) is defined as an AE meeting one of the following outcomes:

- Death during the period of protocol defined surveillance
- Life Threatening Event (defined as a participant at immediate risk of death at the time of the event)
- Inpatient hospitalization or prolongation of existing hospitalization during the period of protocol defined surveillance
- Results in congenital anomaly or birth defect
- Results in a persistent or significant disability/incapacity

Any other important medical event that may not result in one of the above outcomes, may be considered a serious adverse event when, based upon appropriate medical judgment, the event may jeopardize the participant and may require medical or surgical intervention to prevent one of the outcomes listed above. Examples of such medical events include allergic bronchospasm requiring intensive treatment in an emergency room or at home, blood dyscrasias or convulsions that do not result in inpatient hospitalization, or the development of drug dependency or drug abuse.

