8.4 Methods and Timing for Assessing, Recording, Analyzing, and Managing Safety Parameters

8.4.1 Assessment of Safety

General health status and symptom assessments performed at Baseline/Eligibility Visit and Study Visit 1 will serve as baseline for any new signs or symptoms that arise during the study. All such changes occurring after Study Visit 1 will be evaluated as possible adverse events and appropriately recorded on the Adverse Event Case Report Form (CRF).

Baseline and Study Visit 1 assessments are limited to general health history information, pregnancy testing and laboratory assessment for kidney function. Additional safety assessments have been added to include: laboratory evaluations (hematology, blood chemistry, and urinalysis) at pre-specified time points (e.g., pre-treatment, during treatment, and post-treatment). Expected adverse events include possible gastrointestinal (GI) symptoms (nausea, vomiting, constipation, diarrhea, dysphagia).

Subjects will be questioned prior to receiving each study dose and on the last study day for the presence of GI side effects. *See Estimating Severity Grade and method for classifying GI adverse events. Other subject reported symptoms that occur between Study Day 1 and Study Day 18, including the follow up visit at Study Day 29 - 32, will be evaluated as a possible adverse event. If a subject experiences a side effect that requires additional medical attention, the subject will seek medical attention through appropriate standard operating sick call procedures and the medical monitor will be contacted.

Adverse events will be evaluated according to the Estimating Severity Grade and will be recorded on the Adverse Event Log and the Adverse Event CRF. Adverse events deemed greater than Grade 2 will be considered a Serious Adverse Event (SAE). All SAEs will be recorded on the SAE CRF and reported according to FDA and institutional requirements (See Section 8.5 – Specific Serious Adverse Event Reporting Requirements).

Compliance and adverse event reports will be obtained each day that study drug is administered (Study Days 1-18) and at the end of the study (Study Day 29 -32) by the Study Coordinator(s). Each adverse event will be graded according to the Table for Estimating Severity Grade.

For all subjects receiving at least one dose of study drug, the number and percentage of subjects reporting adverse events will be tabulated by cohort and overall by severity and body system.

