| ESTIMATING SEVERITY GRADE | | | | |
|----------------------------------|---|--|---|--|
| Grade 1 (Mild) | Event requires minimal or no treatment and does not interfere with the subject's daily activities | | | |
| Grade 2 (Moderate) | Event results in a low level of inconvenience or concern with the therapeutic measures. Moderate events may cause some interference with functioning. | | | |
| Grade 3 (Severe) | Event interrupts a patient's usual daily activity and may require systemic drug therapy or other treatment. Severe events are usually incapacitating. | | | |
| Grade 4 (Life-Threatening) | Any adverse drug experience that places the patient or participant, in the view of the investigator, at immediate risk of death from the reaction as it occurred, i.e., it does not include a reaction that had it occurred in a more severe form, might have caused death. | | | |
| Grade 5 | Death | | | |
| GASTROINTESTINAL | | | | |
| | Grade 1 | Grade 2 | Grade 3 | Grade 4 |
| Nausea | Mild or transient; maintains reasonable intake | Moderate discomfort; intake decreased significantly; some activity limited | No significant intake; requires IV fluids | Hospitalization required |
| Vomiting | 1 episode in 24 hours | 2-5 episodes in 24 hours | > 6 episodes in 24 hours or needing IV fluids | Physiological consequences requiring hospitalization or requiring parenteral nutrition |
| Constipation | Requiring stool softener or dietary modification | Requiring laxatives | Obstipation requiring manual evacuation or enema | Obstruction or toxic megacolon |
| Diarrhea | Mild or transient; 3-4 loose stools/day or mild diarrhea lasting for less than 1 week | Moderate or persistent; 5-7 loose stools/day or diarrhea lasting > 1 week | > 7 loose stools/day or bloody diarrhea; or orthostatic hypotension or electrolyte imbalance or > 2L IV fluids required | Hypotensive shock or physiological consequences requiring hospitalization |
| Oral discomfort/dysphagia | Mild discomfort; no difficulty swallowing | Some limits on eating/drinking | Eating/talking very limited; unable to swallow solid foods | Unable to drink fluids; requires IV fluids |

All AEs will be reviewed by the Medical Monitor (see Section 8.6) and the Data Safety Monitoring Committee (DSMC). The medical monitor will discuss each adverse event and determine causality in consultation with the Principal Investigator. The degree of certainty about causality will be graded using the categories below:

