8.5 Specific Serious Adverse Event Requirements

The Southern Illinois University School of Medicine is the sponsor for the Investigational New Drug application (IND) filed with the U.S. Food and Drug Administration (FDA). In the interest of subject

safety and to fulfill regulatory requirements, all deaths and life-threatening SAEs due to any cause, which occur during the course of the study must be reported to the Institutional Review Board (IRB) and the Regulatory Affairs Representative within 24 hours after the clinical site becomes aware of the event, and all other SAEs must be reported as soon as possible, but no later than 5 business days. Serious adverse events will be reported to: Dwight D. Eisenhower Army Medical Center (DDEAMC) IRB and to [name] at [contact]. See SAE Reporting procedures, regulatory authority reporting and follow-up under Section 8.6.

In accordance with the FDA Code of Federal Regulations (CFR), the sponsor (Southern Illinois University) must report SAEs that are serious, unexpected, and related to the study intervention to the FDA in the form of a written IND Safety Report. Deaths and life-threatening events with any possible relationship to a study intervention must be reported to the FDA by telephone or fax as soon as possible but within 7 calendar days of IRB awareness. This initial report must be followed by as complete a written report as possible within 8 additional calendar days. All other IND Safety Reports must be submitted to the FDA as soon as possible, but no later than 15 calendar days after IRB is notified of the SAE. SAEs that do not meet the requirements for expedited reporting and all documented adverse events will be reported to the FDA in the IND annual report by the sponsor.

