8.9 Adverse Events (AE) Reporting

We will follow 1996 and 2000 International Conferences on Harmonization, Sections E2 and E6 Good Clinical Practice, HHS and FDA regulations. An adverse event (AE) is defined as any untoward medical occurrence that does not necessarily have a causal relationship with this treatment.

A Serious Adverse Event (SAE) is defined as any untoward medical occurrence that results in death, is life-threatening, requires hospitalization or prolongation of hospitalization, results in persistent or significant disability/incapacity, or is a congenital anomaly or birth defect.

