8.11 Reporting to FDA

Reporting to FDA will be accomplished within the regulatory time frame by the Regulatory Representative. For each adverse event observed, the Principal Investigator must decide whether it meets the definition of a “serious” adverse event. The regulatory definition of a serious adverse event is an event that is fatal or life threatening, results in persistent or significant disability, requires intervention to prevent permanent impairment/damage, or an event that results in congenital anomaly, hospital admission or prolongation of hospitalization. These will be reported within 24 hours by phone and by fax to the Regulatory Representative and submitted to FDA within the regulatory timeframes, and followed up in a timely manner. Regulatory Representative contact information is provided below.

[name]
[contact]
Email: [contact]
[contact]

The Regulatory Representative will confer with the sponsor’s medical monitor prior to submission. The sponsor has not given up the SAE reporting responsibility and will remain responsible for such.

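### Section 8.4.1 makes every event above Grade 2 an SAE while 8.3, 8.9 and 8.11 define SAEs by outcome, and 8.5 and 8.11 set different reporting limits

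*Combined protocol and SAP*

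**What the plan says.** **Classification.** Section 8.3 works from outcomes: "A Serious Adverse Event (SAE) is defined as an AE meeting one of the following outcomes". It then lists death, life threat, inpatient admission, birth defect and lasting disability. It also allows judgment for other important medical events, which "may be considered a serious adverse event when, based upon appropriate medical judgment, the event may jeopardize the participant". Section 8.9 restates the outcome approach without the judgment clause: "A Serious Adverse Event (SAE) is defined as any untoward medical occurrence that results in death, is life-threatening, requires hospitalization", followed by disability and congenital anomaly. Section 8.11 does so again, with one further criterion: "requires intervention to prevent permanent impairment/damage, or an event that results in congenital anomaly, hospital admission or prolongation of hospitalization".

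Section 8.4.1 uses severity instead: "Adverse events deemed greater than Grade 2 will be considered a Serious Adverse Event (SAE". Events caught by that sentence go on the SAE form and follow the reporting route in 8.5.

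**Timing.** Section 8.5 gives 24 hours for deaths and life-threatening SAEs. For the rest, "all other SAEs must be reported as soon as possible, but no later than 5 business days". The recipients are the IRB and the Regulatory Affairs Representative. Section 8.11, speaking of all serious events, says: "These will be reported within 24 hours by phone and by fax to the Regulatory Representative".

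**Grading table.** In 8.4.1, Grade 2 vomiting is 2 to 5 episodes in 24 hours and Grade 3 is "> 6 episodes in 24 hours or needing IV fluids".

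**The concern.** Severity and seriousness are different properties of an event. Severity says how intense the event was; seriousness says what it led to. Section 8.4.1 turns one into the other, and three other sections do not.

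The conflict falls where events are most likely. Section 8.4.1 names gastrointestinal symptoms as the expected adverse events and has subjects asked about them before each dose. Gastrointestinal events also have their own Grade 3 criteria, several of which need no hospital admission. Two coordinators, each following a different section, could therefore record the same event differently.

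Safety and tolerability is a primary objective (1.1.1, 4.2.1), and readers of the final report will look at SAEs by arm. If the active drug did cause more severe gastrointestinal upset, the grade rule would show it as an excess of SAEs, and an outcome definition might not. The SAE label also has operational consequences. It triggers the SAE form and IRB reporting and, under 8.6, an immediate alert to the research monitor and that monitor's written opinion.

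**Working it through.** No sample size, power or event figure is involved, so there is no stated number to reproduce. The check compares the sections and then applies them to specific events.

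**Step 1. The four rules side by side.**

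| Section | Basis for SAE status | Grade trigger | Further clause |
|---|---|---|---|
| 8.3 | Listed outcomes | No | Important medical event, by judgment |
| 8.4.1 | Anything above Grade 2 | Yes | None |
| 8.9 | Listed outcomes | No | None |
| 8.11 | Listed outcomes | No | Intervention to prevent permanent impairment |

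**Step 2. Apply them to events.**

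- *Eight loose stools in a day, no admission.* The table makes more than 7 a day Grade 3, so 8.4.1 makes this an SAE. It meets no outcome listed in 8.3, 8.9 or 8.11. It could be an SAE under 8.3 only through the judgment clause, and under 8.11 only if intervention was needed to prevent permanent impairment.
- *Obstipation treated by manual evacuation or an enema, no admission.* This is also Grade 3, with the same result.
- *Admission for an event graded 2 on the general descriptors.* This is an SAE under 8.3, 8.9 and 8.11, but the grade rule alone does not catch it.

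The first two events show that the grade rule adds SAEs. The third matters only if 8.4.1 is read as replacing 8.3 rather than adding to it.

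**Step 3. The reporting limits.** Take a hospital admission that was not life-threatening. It is an SAE under every outcome definition. Section 8.5 lets the report reach the Regulatory Affairs Representative within 5 business days; 8.11 wants it with the Regulatory Representative within 24 hours. A report sent on the fourth business day complies with 8.5 and breaches 8.11. This assumes that the two titles denote the same role. For deaths and life-threatening events both sections say 24 hours, so there is no conflict.

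**Step 4. The grade boundary, by count.**

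- Vomiting episodes in 24 hours: 1 is Grade 1; 2, 3, 4 and 5 are Grade 2; 6 has no count-based grade; 7 or more is Grade 3.
- Loose stools per day: 3 and 4 are Grade 1; 5, 6 and 7 are Grade 2; 8 or more is Grade 3. There is no count gap.
- Diarrhea lasting exactly one week has no grade by duration, but that lies between Grades 1 and 2 and does not touch the SAE cut.

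The gap is therefore one integer in one row, for a subject who does not need IV fluids or meet a Grade 4 criterion. It falls on the Grade 2/3 cut that 8.4.1 uses.

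**Step 5. Where SAE status enters the plan.** It drives the SAE form (8.4.1), reporting (8.5) and the research monitor's duties (8.6). It does not enter the safety comparison in 10.2, which multiplies frequency by intensity. It does not enter the three stopping rules in 8.7 either. These turn on death, emergency surgery or permanent disability; on an event absent from the consent form; and on an event in more than three subjects.

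**The case against.** The strongest reply is that the sections are compatible. Section 8.4.1 can be read as a deliberately cautious addition to 8.3: it removes no event that 8.3 captures, and over-reporting is safer than under-reporting. Section 8.3 is not a closed list, so some Grade 3 events, such as those with bloody diarrhea or electrolyte imbalance, could be judged important medical events anyway. The two deadlines are upper limits, and reporting within 24 hours satisfies both. Severe events will be visible regardless, because 8.4.1 already tabulates adverse events by severity and body system. Extra gastrointestinal SAEs would not ordinarily become IND Safety Reports, because 8.5 limits those to events that are serious, unexpected and related, and 8.4.1 lists these symptoms as expected. Finally, the general Grade 1 to 5 descriptors above the gastrointestinal rows can grade six vomiting episodes by their effect on the subject.

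Much of this stands, and it limits the point. A reader might infer that no Grade 3 gastrointestinal event without a listed outcome could be an SAE outside 8.4.1. The documents do not support that, because 8.3 leaves room for judgment and 8.11 has its intervention criterion. The difference is between automatic and discretionary classification.

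The reply does not remove the conflict. Nothing in 8.4.1 says that it adds to 8.3, and 8.9 and 8.11 restate definitions without a grade. Even on the additive reading, applying 8.4.1 gives an SAE count at least as large as applying 8.9 or 8.11, and larger once any Grade 3 event lacks a listed outcome or the 8.11 criterion. That a single practice could satisfy both deadlines does not tell the site which one it is held to.

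**Conclusion.** The point holds as an internal inconsistency that should be corrected. SAE classification differs between 8.4.1 and the three outcome-based sections, so SAE counts and listings depend on the section followed. The deadline conflict is separate, concerns timing only, and is confined to SAEs that are neither fatal nor life-threatening. It rests on the assumption that the two representative titles are one role. The vomiting gap is minor. It is the same whichever section is followed, so it does not contribute to the dependence on section.

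Two stronger readings are tempting and not supported. A reader might infer a definite number of misclassified events. The documents give no Grade 3 rate; the only finding quoted for healthy subjects is that Phase 1 saw no side effects (2.6). Any figure would be the analyst's own assumption multiplied by 600. A reader might also infer that the primary safety result or the stopping decision is compromised. Neither the 10.2 test nor the 8.7 rules refer to SAE status. The most that can be said is that an ungraded vomiting event could lack an intensity score in 10.2, if intensity is taken from this table and the general descriptors are not used.

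**What to change.** 1. Record severity grade and seriousness as separate fields on the adverse event form.
2. Reconcile 8.3, 8.4.1, 8.9 and 8.11 to one SAE definition, and use it for the SAE form, for reporting and for all tables. If a grade-based rule is kept for operational reporting, say so and keep it distinct from the SAE definition.
3. Show Grade 3 or higher events by arm within the severity tabulation that 8.4.1 already plans. That section says by cohort and overall, while the synopsis says by treatment group, so the arm split should be stated.
4. Reconcile the limits in 8.5 and 8.11, and use one title for the representative.
5. Have the sponsor assign a grade to exactly six vomiting episodes in 24 hours.
6. Because enrollment is under way (section 13.0), reclassify events already on the SAE form under the settled definition, blind to arm.

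The cost is protocol and form wording plus a short blinded review of recorded events. No new assessment, subject or analysis is needed.

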8.5 Specific Serious Adverse Event Requirements

The Southern Illinois University School of Medicine is the sponsor for the Investigational New Drug application (IND) filed with the U.S. Food and Drug Administration (FDA). In the interest of subject

safety and to fulfill regulatory requirements, all deaths and life-threatening SAEs due to any cause, which occur during the course of the study must be reported to the Institutional Review Board (IRB) and the Regulatory Affairs Representative within 24 hours after the clinical site becomes aware of the event, and all other SAEs must be reported as soon as possible, but no later than 5 business days. Serious adverse events will be reported to: Dwight D. Eisenhower Army Medical Center (DDEAMC) IRB and to [name] at [contact]. See SAE Reporting procedures, regulatory authority reporting and follow-up under Section 8.6.

In accordance with the FDA Code of Federal Regulations (CFR), the sponsor (Southern Illinois University) must report SAEs that are serious, unexpected, and related to the study intervention to the FDA in the form of a written IND Safety Report. Deaths and life-threatening events with any possible relationship to a study intervention must be reported to the FDA by telephone or fax as soon as possible but within 7 calendar days of IRB awareness. This initial report must be followed by as complete a written report as possible within 8 additional calendar days. All other IND Safety Reports must be submitted to the FDA as soon as possible, but no later than 15 calendar days after IRB is notified of the SAE. SAEs that do not meet the requirements for expedited reporting and all documented adverse events will be reported to the FDA in the IND annual report by the sponsor.

or serious adverse events. Unanticipated problems and adverse events will be reported to the IRB in accordance with institutional policy and to the FDA as required. Data and safety monitoring reports will be provided to the IRB at the time of continuing review per DDEAMC policy.

The investigators, research monitors, coordinator(s) and data manager of this protocol will meet at least once per month via videoconference or teleconference to review the following: study progress (including data quality and timeliness, recruitment, accrual and retention), study procedures (including subject privacy and data confidentiality protection), outcomes of adverse events and new literature reviews to assess change to the risk/benefit ratio and to determine if modifications need to be made or the study terminated. The Regulatory Representative ([name]) will be included via teleconference to assess the regulatory impact of outcomes of adverse events and new literature reviews to assess change to the risk/benefit ratio and to determine if modifications need to be made or the study terminated..

8.7 Stopping Rules Based on Adverse Events

The safety of individual research subjects is of primary importance in this study as hearing loss does not result in serious morbidity or mortality and the active drug is considered relatively benign. Thus, for this study, the following stopping rules for safety will be utilized:

1. The study will be stopped if any subject dies, if any subject requires emergency surgery, or if any subject suffers a permanent and irreversible disability, unless it can be shown that this event was unrelated to participation in the clinical trial.
2. Should an adverse event occur that is not mentioned in the consent form, then the study will be stopped until both the consent form has been revised to include this adverse event and the institutional review board (IRB) gives re-approval of the study. The adverse event will also be reported to the FDA as it impacts safety.
3. If an adverse event that is not covered under item 1 occurs in more than three subjects, then the risk of the adverse event associated with the active drug group will be compared to the risk of the adverse event associated with the placebo group. If the rate is significantly higher for the active drug group at an unadjusted confidence level of 95% (i.e., alpha level of 0.05), then the data safety monitoring committee (DSMC) will be required to determine, based on the severity of the adverse event, if the trial should be stopped for safety.

8.9 Adverse Events (AE) Reporting

We will follow 1996 and 2000 International Conferences on Harmonization, Sections E2 and E6 Good Clinical Practice, HHS and FDA regulations. An adverse event (AE) is defined as any untoward medical occurrence that does not necessarily have a causal relationship with this treatment.

A Serious Adverse Event (SAE) is defined as any untoward medical occurrence that results in death, is life-threatening, requires hospitalization or prolongation of hospitalization, results in persistent or significant disability/incapacity, or is a congenital anomaly or birth defect.

